2020-09-02 NCT 05772299

RESEARCH PROPOSAL

Treatment of peri-implant mucositis using an Er: YAG laser or an ultrasonic device. A randomized clinical trial.

Background and Significance

Peri-implantitis is an inflammatory process resulting in loss of supporting bone whereas peri-implant mucositis has been defined as a reversible inflammatory change of the peri-implant soft tissues without bone loss (Renvert et al 2018, Berglund et al. 2018). The prevalence of peri-implant mucositis and peri-implantitis ranged from 19 to 65% and from 1 to 47%, respectively. Meta-analyses estimated weighted mean prevalence's of peri-implant mucositis and peri-implantitis of 43% (CI: 32–54%) and 22% (CI: 14–30%), respectively (Derks et al. 2015). With an increasing population with dental implants the prevalence of implant related infections will increase and cause major challenges to the profession and society.

Approximately 65% of all infectious diseases are associated with biofilms including periodontal and peri-implant infections (Costerton et al. 1999, Lamont and Jenkinson 2000, Socransky & Haffajee 2005, Lee et al. 1999, Leonhardt et al. 2003, Roos-Jansåker et al. 2003). Bacterial colonization on oral implant surfaces occurs rapidly (Quirynen et al. 2006, Fürst et al. 2007, Salvi et al. 2007). The development of a tightly fixed layer of plaque, the so-called bio-film is critical and would in principle cause an irreversible binding to the implant surface (Lamont and Jenkinson 2000). The goal with non-surgical therapy of peri-implantit mucositis is to eliminate or significantly reduce the levels of pathogens to a level allowing healing and a clinically healthy situation.

Eradication of pathogens by mechanical means on the implant surface with threads and often a rough surface structure may be difficult using conventional means of therapy. Dental implants have generally a screw shaped design and in order to facilitate healing and osseo integration the surface structure is often rough. In case of infection and microbial colonization of the implant surface these features, positive for the initial stabilization and healing of the implant, becomes treatment complicating factors. Treatment models effectively used to treat the root surfaces of the tooth with periodontal disease like scaling and root-planning are difficult to use on the rough threaded implant surface. This surface gives the micro organisms "protected areas" with the roughness of the surface. In a consensus paper on the treatment of periimplant mucositis it was concluded that" It has not been documented that mechanical

2

therapy alone is effective in reducing bleeding o probing" (Lindhe & Meyle 2008). Accordingly, methods have been aiming at eradication of the micro-organisms from a distance. In this aspect, the adjunct of local antibiotics has been attempted. (i.e. Flemmig 1994, Kao et al. 1997, Lang et al. 1997, Porras et al. 2002, Renvert et al. 2004,2006, Persson et al. 2006, Jorgensen et al. 2004, Bonito et al. 2005, McColl et al. 2006). The adjunct effects using local antibiotics are, however, not conclusive.

Another new treatment model, the use of lasers has been proposed for the treatment of peri-implant mucositis and peri-implantitis. The use of a laser can be considered a minimally invasive technique, that may result in less discomfort than traditional mechanical treatment approaches. Furthermore, lasers may have bio stimulatory effects that are reported to result in better wound healing compared to traditional approaches and in periodontal tissue regeneration (Aoki et al. 2004). In an experimental peri-implantitis model in dogs, it was demonstrated that favorable formation of new bone was observed on the laser-treated implant surface, and the laser group showed a tendency to produce greater bone-to-implant contact than the curette group (Takasaki et al. 2007). In a randomized clinical trial comparing the use of an Er:YAG laser and an air abrasive device in the treatment of peri-implantitis it was found that bleeding on probing (BOP) and suppuration (SUP) decreased in both the groups (p<0.001). The mean probing depth (PPD) reductions in the air abrasive and laser treated groups were 0.9mm (SD \pm 0.8) and 0.8mm (SD \pm 0.5) (Renvert et al. 2011).

In a recent review of the evidence using lasers in the treatment of peri-implant diseases it was concluded that the current evidence shows laser therapy in combination with surgical/nonsurgical therapy provided minimal benefit in Pocket depth (PD) reduction and clinical attachment (CAL) but when adjunct to non-surgical therapy might result in more BOP reduction in the short term (Lin et al. 2018). It was also concluded that data on adjunctive laser treatment for peri-implant mucositis are

scarce. Therefore, future clinical trials are needed to evaluate the potential benefit of this approach.

In summary, peri-implant mucositis is a very common clinical entity in patients with dental implants. This inflammation in the peri-implant mucosa may develop into peri-implantitis and result in implant loss. Early and effective treatment of peri-implant

mucositis is therefore an important continuous task for the dental professions. It is imperative to perform randomized trials comparing treatment alternatives to control implant infections. The present research project is designed to compare a conventional non-surgical approach using an ultrasonic device with an Er: YAG laser device (Morita Corporation, Japan) Clinical outcome measures of therapy will be used under observer masked conditions.

Specific aims

To assess the clinical outcome over 6 months following treatment with non-surgical debridement using a Er: YAG laser device (AdvErL EVO, Morita corporation, Japan) or with the use mechanical therapy using ultrasonic device with a specially designed tip (EMS, Switzerland)

Materials and methods

Outcome variables

- The extent of gingival inflammation (bleeding on probing BOP)
- Clinical probing pocket depth values
- Clinical registration of suppuration
- Recession of the peri-implant mucosal margin at test and control sites between baseline and at study endpoint (6 months)
- The treatment times
- Changes in "bone levels" (measured from periapical radiographs (see below)
- The prevalence of implant loss

Subject screening

Exclusion criteria

- Subjects with uncontrolled diabetes mellitus (HbA1c > 6.5)
- Subjects requiring prophylactic antibiotics
- Subjects taking prednisolone
- Subjects taking medications known to have effects on gingival growth

• Subjects with a history of taking systemic antibiotics in the preceding 1 month

Inclusion criteria - Presence of peri-implant mucositis

Following a review of the medical history (see exclusion criteria) a full mouth routine periodontal examination, including analysis of available radiographs, will be performed. Subjects who consent and:

- Have a minimum of one or more peri-implant sites with probing depth ≥ 4 mm combined with bleeding and/or pus on probing using 0.2 N probing force.
- 2. No peri-implant marginal bone loss (as determined from a comparison of the bone level one year following implant reconstruction with the bone level at screening (screening radiograph)
- A limited allowed bone loss ≤ 2mm measured from the implant shoulder (as a consequence of remodeling during the healing process)

Intraoral radiographs

Intraoral standardized radiographs of the site of interest will be taken at baseline and at 6 months. Radiographs will be analysed by an independent and blinded examiner.

Treatment procedure

Baseline measurements will be performed, and the patients are randomized into treatment groups A or B. The treatment will be performed by a dentist not involved in the registrations in order to avoid bias. Following treatment, the patients will be instructed in proper homecare using a toothbrush and interproximal aids as needed.

Group A will be treated using the ER: YAG laser device (AdvErL EVO, Morita Corporation, Japan). The tip is placed in the pocket mesially, lingually, distally and buccally. Careful attempts are to cover the full circumference of the implant. Moving motion would be from bottom to coronal, sweeping motion also covering the soft tissue surface.

Group B will be treated using an ultrasonic device with PEEK coated tips (EMS, Switzerland). The tip is placed in the pocket mesially, lingually, distally and buccally. Careful attempts are to cover the full circumference of the implant.

Material and settings

The device used for the clinical study for Group A will be an Er:YAG laser device (AdvErL EVO, J. MORITA MFG. CORP., Japan) using a below prameter. Group B will receive standard of care using an ultrasonic device with plastic coated tips.

Parameter of Er:YAG laser AdvErL EVO (on the display)

Tip:PS400T Power:30-50mJ Frequency:10PPS Air/Water:7/7

Patient entry

The study will be submitted to the Ethics committee in Uppsala and written consent will be obtained from all subjects to be entered in the study. Once the entry criteria have been confirmed the subject will be entered to the study and assigned a patient number.

After having been entered into the study, subjects will be randomly assigned to one of the two treatment regimens. Random assignment will be performed according to predefined randomisation.

Subject protection – monitoring of adverse events

At each visit the clinician will evaluate patients for any adverse events. Should a patient require any treatment during the course of the study, the necessary treatment will be provided at the discretion of the clinician and according to the current standard of care. All adverse events related to the treatment provided will be recorded. The investigation will be performed according to the principles of the Declaration of Helsinki on experimentation involving human subjects.

Measurements

One and the same examiner, unaware of treatment group for the patient, will perform all the measurements. Before treatment the following baseline measurements will be recorded:

- 1. Intraoral photographs of the implant site
- 2. Presence/absence of hyperplasia
- 3. Full mouth plaque score (FMPS). Presence of dental plaque along the gingival/mucosal margin recorded after use of disclosing dye and expressed as a percentage of examined sites within each patient (4 sites per tooth and implant).
- 4. Local Plaque Score. Presence of dental plaque along the mucosal margin at 6 sites of each treated implant recorded after use of disclosing dye and expressed as a percentage of implant sites within each patient.
- 5. Probing pocket depths (PPD) at the implant (6 sites/implant). Recorded at 6 sites of each treated implant to the nearest mm using a plastic probe.
- Recession of the mucosal margin relative to the restoration margin (REC) at the implant buccally. Position of the mucosal margin apical to the restoration margin is positive recession (+), position of the mucosal margin coronal to the restoration margin is negative recession (-).
- Bleeding on probing (BOP) graded 0-3 at the implant (6 sites/implant). Bleeding appearing after measurement of probing depth and expressed as: 0=no bleeding, 1=a dot of bleeding, 2=a line of bleeding, 3=a drop of bleeding
- 8. Presence /absence suppuration (SUP) at the implant (6 sites/implant).
- 9. Presence/absence of bleeding on probing (BOP) at all teeth/implants (4 sites)
- 10. Treatment times
- 11. Patient evaluation of the treatment: Visual analog scale for pain during treatment, the same day after treatment, one day after treatment and three days after treatment. Visual analog scale for aesthetic/satisfaction before the baseline examination and before the examination at 6 months. Postoperativ complications

is asked for in the examination protocol as an open question. Oral health impact profile is measured with the OHIP-14 version.

- All probing measurements will be made using a manual plastic probe.
- Clinical indices concerning probing pocket depths (PPD), bleeding on probing (BOP), plaque and suppuration will be recorded as 6 sites per implant: mesiobuccal, mid-buccal, disto-buccal, disto-lingual, mid-lingual, mesio-lingual.
- Full mouth plaque scores (FMPS) will be recorded as the percentage of total surfaces (4 aspects per tooth/implant) that revealed the presence of plaque (O'Leary et al. 1972). Full mouth bleeding scores (FMBS) will be recorded as the percentage of total surfaces (4 aspects per tooth/implant) that revealed the presence of bleeding.

Statistical power analysis

If BOP is reduced to 30 % \pm 10 in Group A and with 30 % decrease in group B is to be detected at α = 0.05 and a power of β = 0.2, the appropriate number of subjects would be around n = 38. Hence, it is foreseen to incorporate 45 subjects in the study if some of the individuals will not fulfil the study.

Allocation concealment

Assignment to test and control group will be made using pre-prepared randomization in groups A or B. Cards with group identification will be prepared and placed in numbered envelopes after randomization. This will be done by a person not involved in the treatment or diagnosis of patients. As a new patient is admitted to the study the treating clinician takes the next numbered envelope then assigning the patient to either group A or B. The code for treatment A and B will be broken once the study is completed and the data set is locked.

Clinical registrations and treatment at baseline

- Clinical photo
- Presence/absence of plaque (6 sites/implant)
- PPD (6 sites/implant)

- Recession of the buccal mucosal margin
- BOP (6 sites/implant) graded
- Presence/absence of suppuration (6 sites/implant)
- FMPS (4 sites per tooth/implant)
- FMBS (4 sites per tooth/implant)
- Prescence/absence of hyperplasia
- Radiograph of the treated site
- Oral hygiene instruction + subgingival treatment in accordance to randomization
- Patient evaluation of the treatment including a VAS scale for pain. And another for aesthetic/satisfaction. OHIP-14 for quality of life assessment in relation to oral health.

Clinical registrations - 1 month

- Clinical photo
- Presence/absence of plaque (6 sites/implant)
- PPD (6 sites/implant)
- BOP (6 sites/implant) graded
- Presence/absence of suppuration (6 sites/implant
- FMPS (4 sites per tooth/implant)
- Re-instructions in oral hygiene procedures

Clinical registrations and supportive treatment at 3 months

- Clinical photo
- Presence/absence of plaque (6 sites/implant)
- PPD (6 sites/implant)
- Recession of the buccal mucosal margin
- BOP (6 sites/implant) graded
- Presence/absence of suppuration (6 sites/implant)

- Presence/absence of hyperplasia
- FMPS (4 sites per tooth/implant)
- FMBS (4 sites per tooth/implant)
- Oral hygiene instruction + subgingival treatment in accordance to randomization
- Patient evaluation of the treatment including a VAS scale for pain.

Clinical registrations and therapy at 6 months

- Clinical photo
- Presence/absence of plaque (6 sites/implant)
- PPD (6 sites/implant)
- Recession of the buccal mucosal margin
- BOP (6 sites/implant) graded
- Presence/absence of suppuration (6 sites/implant)
- Presence/absence of hyperplasia
- FMPS (4 sites per tooth/implant)
- FMBS (4 sites per tooth/implant)
- Radiograph of the treated site.

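### Adverse events are sought without restriction, but the commitment to record covers only treatment-related ones, with no named assessor of relatedness and no adverse-event summary in the SAP

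*Protocol*

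**What the plan says.** The protocol section on subject protection and adverse-event monitoring uses two scopes. Looking for events is unrestricted: "At each visit the clinician will evaluate patients for any adverse events". The commitment to record is narrower: "All adverse events related to the treatment provided will be recorded".

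Between these two sentences stands one about care that a patient may need during the study, for which "the necessary treatment will be provided at the discretion of the clinician and according to the current standard of care". The recording sentence then refers again to treatment provided, without saying whether it means the study device or this other care.

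On who knows the allocation, the Allocation concealment section says that "the treating clinician takes the next numbered envelope then assigning the patient to either group A or B". The Measurements section says: "One and the same examiner, unaware of treatment group for the patient, will perform all the measurements". Neither role is named as the assessor of relatedness.

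Some harm-relevant data are collected with no stated causality condition. Item 11 of Measurements has "Visual analog scale for pain during treatment, the same day after treatment, one day after treatment and three days after treatment", and says that postoperative complications "is asked for in the examination protocol as an open question". The outcome list includes "The prevalence of implant loss", as well as suppuration, recession and bone-level change. The SAP does not mention adverse events.

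**The concern.** If the recording sentence is followed as written, an event has to be judged related before it need be entered. An event judged unrelated need leave no trace as an adverse event, so nobody can revisit the judgement later.

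Two things are at stake. The first is completeness: the count by arm becomes a count of attributed events. The second is comparability: attribution may differ by device. The protocol's background suggests that the laser may cause less discomfort than mechanical treatment, and the ultrasonic arm is described as standard of care. Such expectations could affect attribution in either direction. The result could be a difference in recorded harm where none exists, or a real difference that is masked.

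**Working it through.** The documents give no adverse-event rate and no relatedness probability, so there is no figure of the plan's own to reproduce. The check has two parts.

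**1. The text**

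- *Scope.* Evaluation covers any event; recording covers related events. The word *only* does not appear, but no sentence in either document commits to recording the others. The visit checklists contain no adverse-event line.
- *Assessor.* The section says just that a clinician evaluates patients. The treating clinician learns the allocation from the envelope; the examiner is masked. Which of them judges relatedness is not stated, and no criteria are given.
- *What escapes the filter.* Pain, the complications question, suppuration, recession, bone level and implant loss. Suppuration and recession are among the measurements made by the masked examiner, and radiographs are read by a blinded one.
- *What does not.* Unexpected or non-local events that fit none of these items. The complications question sits under patient evaluation of treatment. The visit lists show that evaluation at baseline, 3 and 6 months but not at 1 month, and the timing of the question itself is not given.

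**2. The possible size (all rates assumed)**

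Let p be the true event rate in an arm and r the share of events judged related.

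Recorded rate = p × r

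Recorded ratio = true ratio × (r in one arm ÷ r in the other)

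With the same true rate in both arms:

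| True rate, both arms | r = 0.9 vs 0.6 | r = 0.8 vs 0.4 | r = 0.8 vs 0.8 |
|---|---|---|---|
| 10% | 9% vs 6% | 8% vs 4% | 8% vs 8% |
| 20% | 18% vs 12% | 16% vs 8% | 16% vs 16% |
| 30% | 27% vs 18% | 24% vs 12% | 24% vs 24% |
| Recorded ratio | 1.5 | 2.0 | 1.0 |

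For the 20% row with 0.9 versus 0.6: 0.20 × 0.9 = 0.18 and 0.20 × 0.6 = 0.12, a ratio of 0.18 ÷ 0.12 = 1.5. Planned enrolment is 45; assuming 1:1 allocation, that is about 22 per arm. The true expectation is then 22 × 0.20 = 4.4 events per arm, against 22 × 0.18 = 4.0 and 22 × 0.12 = 2.6 recorded.

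The filter can also hide a difference. True rates of 20% and 30%, with r of 0.9 and 0.6 respectively, both record as 18% (0.20 × 0.9 = 0.30 × 0.6 = 0.18).

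The last column shows the limit of the argument: equal filtering shrinks the counts but creates no false ratio.

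**The case against.** The strongest reply is that most of the harm one would expect from two local debridement devices is captured elsewhere, in both arms, without a causality condition and partly by masked assessors. That stands. A reader might infer from the recording sentence that the devices cannot be compared fairly on harm at all. The documents do not support this, because the six items listed above remain available for comparison.

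A reader might also infer that an unmasked clinician makes the relatedness judgement. This is not established either: the treating clinician knows the device, but the protocol does not say that this person judges relatedness, and it keeps the treating dentist out of the registrations. The supportable criticism is that the assessor is not named.

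The illustrative shares come from nowhere in the documents, and a false difference needs unequal filtering. That stands too; the table shows what could happen, not what is likely.

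Finally, the trial is too small for a formal comparison of adverse events even with complete recording. At about 22 per arm and a two-sided 0.05 level, power is about 15% for 10% versus 20%, and 38% for 10% versus 30%. Zero events in 22 patients would still allow a true rate up to 1 − 0.025^(1/22) = 15.4% (upper end of the exact two-sided 95% interval). These figures reflect sample size, not the filter, and they support a descriptive table instead of a test. They do not excuse incomplete recording, since complete description is the main thing so small a trial can offer on harm.

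**Conclusion.** The point holds in a limited form. The protocol's stated rule makes relatedness the condition for recording an adverse event, leaves unclear which treatment is meant, and names no assessor; the SAP plans no summary. Adverse-event counts may be incomplete for other or unexpected events.

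A false difference between arms is possible but conditional on attribution that differs by device. Under the assumed shares it is 3 to 9 percentage points for 0.9 versus 0.6, and 4 to 12 points for 0.8 versus 0.4, over true rates of 10% to 30%. With equal shares it is zero. The conclusion about incomplete recording rests on the text alone and needs none of these assumptions.

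**What to change.** In the protocol, replace the recording sentence with one to this effect: *All adverse events, whether or not considered related to the study treatment, are recorded at every visit with date, site, severity and action taken; relatedness to the study treatment is entered as a separate item by the assessor named here.* Name that assessor by role, masked where existing staff allow. The reference to the study treatment also removes the ambiguity left by the preceding sentence.

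In the SAP, add a descriptive table of all adverse events by randomised group with exact 95% confidence intervals, and show related events as a subset. The all-events rows should lead, because the related subset still depends on the attribution judgement.

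The cost is one extra form field, a longer event list and one extra table, with no additional visits. The change has to be in force while data are being collected, since events that were never written down may not be recoverable.

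### The masked examiner's task list includes treatment times and an open complications question, so masking of the follow-up BOP and PPD is not secured as written

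*Protocol*

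**What the plan says.** The protocol's Background and Significance section sets the intention: "Clinical outcome measures of therapy will be used under observer masked conditions". The Measurements section carries it out with one sentence: "One and the same examiner, unaware of treatment group for the patient, will perform all the measurements".

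The next sentence opens a numbered list: "Before treatment the following baseline measurements will be recorded". The list contains the observer-dependent clinical scores, among them "Bleeding on probing (BOP) graded 0-3 at the implant (6 sites/implant", and probing depth read with a manual plastic probe. It also contains:

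- "10. Treatment times";
- under patient evaluation, "Visual analog scale for pain during treatment, the same day after treatment, one day after treatment and three days after treatment";
- post-operative complications, which the text says "is asked for in the examination protocol as an open question".

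Treatment time is also one of the named outcome variables, so somebody must record it. The Treatment procedure section says that the dentist who gives the treatment takes no part in the registrations, as a guard against bias. Under Allocation concealment, the treating clinician opens the envelope, and the A/B code is broken only after the data are locked. Radiographs go to a separate blinded reader.

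**The concern.** The operator knows the arm. The documents do not say whether patients are masked or are asked not to reveal their treatment. Masking of the examiner is therefore the main stated safeguard against detection bias in BOP and PPD. BOP matters most, because it is the variable on which the sample size is based in both the protocol and the SAP. It is graded by eye as dot, line or drop, which leaves room for judgement.

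Two items on the examiner's list work against that safeguard. A person who times a session in person sees a laser or an ultrasonic device. A person who asks a patient an open question about complications may hear the treatment described. The examiner then carries that knowledge into every later probing of the same patient.

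**Working it through.** **Step 1: who can record treatment time?** No figure in the documents tests this, so the statements are set side by side.

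| Source (protocol) | Treating dentist | Masked examiner |
|---|---|---|
| Treatment procedure | Gives treatment; no part in registrations | – |
| Measurements, opening sentence | – | Makes every measurement; must not know the arm |
| Measurements, item 10 | – | Treatment times are on this list |

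The first row rules out the dentist. The second and third give the task to the examiner, who cannot do it in person and stay masked. The documents name nobody else for it. The role statements conflict.

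**Step 2: who asks about complications, and when?** The item is on the examination form. Neither the asker nor the visit is stated. The adverse-event section refers only to the clinician at each visit, without saying whether that is the examiner or the treating dentist.

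**Step 3: which scores are exposed?**

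- Baseline: BOP and PPD are recorded before treatment, so they are not exposed.
- 1 month: no treatment is listed at this visit, but the examiner may have timed the baseline session.
- 3 months: probing is listed before the repeat treatment and the VAS, but the baseline session is already past.
- 6 months: the order is the same, with the baseline and 3-month sessions already past.

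The order within a visit therefore does not protect a later visit from a session timed earlier.

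**Step 4: illustration of size.** From the documents: 38 subjects, ±10 for BOP, 6 sites per implant, and an unequal-variance t-test at 0.05 (SAP). Assumed: 38 is the total, split 19 and 19; ±10 is an SD in percentage points; one implant per patient; no true difference; and one site misscored, always in the same direction, in a random fraction *p* of one arm.

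- One site of six: 100/6 = 16.7 points.
- Shift in the arm mean: 16.7 × *p* = 4.17 points at *p* = 1/4, and 2.08 points at *p* = 1/8.
- SD in the affected arm: √(10² + 16.7² × *p*(1 − *p*)) = √(100 + 52.1) = 12.3 at 1/4, and √(100 + 30.4) = 11.4 at 1/8.
- SE of the difference: √((152.1 + 100)/19) = 3.64 at 1/4, and √((130.4 + 100)/19) = 3.48 at 1/8.
- Shift in SE units: 4.17/3.64 = 1.14, and 2.08/3.48 = 0.60.
- Simulated two-sided rejection rate with the unequal-variance t-test: about 19% at 1/4, and between 8% and 9% at 1/8, against 5% with no bias.

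This models the percentage of sites that bleed. On the 0–3 grade, a change from 1 to 2 would not move that percentage at all.

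**The case against.** The strongest reply is that this is loose drafting. The list is headed as baseline and pre-treatment, which cannot be true of treatment times, pain after treatment or post-operative complications, so those items look appended rather than deliberately given to the examiner. Radiographs already have their own reader, so the word all is not meant literally. The separate dentist, the envelope procedure and the late code break show that masking was thought about. That is fair, and it means the blind may well hold in practice. It does not resolve who times treatment, and a site following the text has no other instruction.

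A reader might also infer more than the documents support:

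- *That the blind is impossible.* This follows only if the examiner times sessions in person. A time in minutes passed on by someone else does not by itself name the arm.
- *That the pain VAS unmasks.* This is a weak route. It is a patient rating, with points at one and three days when no visit is scheduled, so it is probably self-completed. A pain score names no device.
- *That patients are known to be unmasked.* Their masking status is not stated.
- *That nothing puts probing first.* The 3- and 6-month lists do place it before treatment and the VAS. That is list order rather than a stated rule, and it does not help against a session timed earlier.
- *That the false-positive rate would be about 24% or 10%.* Those figures come from treating the bias as a constant shift with SE 10√(2/19) = 3.24. Misscoring a random fraction of patients also adds variance, which lowers the rates to those shown in the working.

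**Conclusion.** The point holds as a conflict in role assignment: masking of graded BOP and PPD at 1, 3 and 6 months is not secured as written. Treatment timing is the clear conflict, and the open complications question is a plausible second route. Baseline scores are unaffected.

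The conclusion rests on the text and on no number. Its size cannot be estimated, because the documents give no rate or direction of bias. The 19% and the 8% to 9% show only that modest one-directional misscoring would matter in a trial of this size. They are not a prediction. The documents do not show that the examiner will in fact be unmasked. It is worth correcting because the stated masking is sound in intent and the correction is nearly free.

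**What to change.** 1. In Measurements, limit the masked examiner to the clinical indices: plaque, PPD, recession, BOP, suppuration, hyperplasia and photographs.
2. Move treatment times and the complications question to a separate form kept by the treating dentist or other existing staff who know the arm. Have patients complete the VAS and OHIP-14 themselves.
3. In Treatment procedure, define registrations as the clinical indices. Without this, asking the treating dentist to record treatment time would contradict that section.
4. State that at each follow-up visit the examiner completes probing before any conversation about treatment, and has no access to the separate form.

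The cost is protocol wording and one form split in two, with no extra staff or visits. There are two small downsides. Someone who knows the arm must briefly see the patient at 1 month, after probing. Complications will also be recorded by a person who is not masked; that trade-off should be acknowledged in the protocol.
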